9.4.3 Safety

[Part A/Part B/Part C]

All safety analyses will be performed on the safety analysis set. Safety variables are AEs, vital signs, 12-lead ECGs, and laboratory assessments. All safety data (scheduled and unscheduled) will be presented in the data listings.

Safety variables will be summarised by treatment group and visit using descriptive statistics (n, mean, SD, median, minimum and maximum [and geometric mean and coefficient of variation, if applicable]) for continuous data and absolute and relative frequencies for categorical data.

Adverse events will be summarised by Preferred Term and System Organ Class using MedDRA terminology. Adverse events that led to withdrawal, SAEs, AEs by severity, and causally related AEs will also be presented. All AE summaries will be done by treatment group.

Injection site reactions will be considered an AE of special interest and will be listed.

Clinical laboratory data and ECG parameters will be summarized by treatment group and visit.

Use of concomitant medication will be reported.

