3.3 General Considerations

There is no formal statistical hypothesis testing in this study. Safety and tolerability after multiple dosing of AZD8233 [REDACTED] (or placebo) will be descriptively evaluated. The following principles will be followed throughout the study:

- Continuous variables will be summarized by the number of non-missing observations, mean, standard deviation (SD), median, first and third quartiles, and the minimum and maximum as appropriate.
- Log-transformed continuous variables will be summarized in a similar manner where applicable. In addition, the relative change from baseline will be calculated by back-transforming the change from baseline of the logarithmic variable.
- Categorical variables will be summarized as counts (n) and percentages (%). Unless otherwise stated, percentages will be calculated using the relevant analysis set population total as the denominator. Percentages will not be presented for zero counts.
- Mean and medians will be rounded to one additional decimal place relative to the original data, the SD will be rounded to two additional decimal places, and the maximum, minimum and quartiles will be displayed with the same accuracy as the original data. 95% confidence intervals (CIs) will be presented to one more decimal place than the raw data. Percentages (proportion) will be rounded to one decimal place.
- Summaries will be provided by study visit where appropriate. Where summaries are over time, study day will be calculated in relation to the date of first dose of study treatment.
- Corresponding listings will be provided for all tabulated results unless stated otherwise. Any additional listings that are required will be described in the appropriate sections of the SAP.
- SAS® version 9.3 or higher will be used for all data analyses.

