Visit 6 (Day 29)	Day 29	Day 19 – Day 42
Visit 9 (Day 57 to 59)	Day 57 to Day 59	Day 43 – Day 63
Follow-up period		
Visit 10 (FUP Week 2)	Day 71	Day 64 – Day 77
Visit 11 (FUP Week 4)	Day 85	Day 78 – Day 91
Visit 12 (FUP Week 6)	Day 99	Day 92 – Day 105
Visit 13 (FUP Week 8)	Day 113	Day 106 – Day 119
Visit 14 (FUP Week 10)	Day 127	Day 120 – Day 133
Visit 15 (FUP Week 12)	Day 141	Day 134 – Day 147
Visit 16 (FUP Week 14)	Day 155	Day 148 – Day 161
Visit 17 (FUP Week 16)	Day 169	Day 162 onwards.

^a Baseline is defined as the last measurement prior to first dose of study treatment. Pre-dose values on Day 1 qualify as baseline measurements.

^b Day 1 is defined as date of first dose of study treatment.

Table 3: Analysis visit window for laboratory results and anti-AZD8233 antibodies

Analysis Visits	Scheduled visit day	Analysis visit window (days)
Baseline ^a	Day -28 to Day 1	≤ Day 1
Treatment period		
Visit 2 (Days 1 to 3) ^{c, e}	Days 1 to 3	Day 1 ^b – Day 3
Visit 3 (Day 8)	Day 8	Day 4 – Day 18
Visit 6 (Day 29) ^e	Day 29	Day 19 – Day 42
Visit 9 (Day 57 to 59) ^{c, e}	Day 57 to Day 59	Day 43 – Day 63
Follow-up period ^d		
Visit 10 (FUP Week 2) ^e	Day 71	Day 64 – Day 77
Visit 11 (FUP Week 4)	Day 85	Day 78 – Day 98
Visit 13 (FUP Week 8)	Day 113	Day 99 – Day 126
Visit 15 (FUP Week 12)	Day 141	Day 127 – Day 154
Visit 17 (FUP Week 16) ^e	Day 169	Day 155 onwards.

^a Baseline is defined as the last measurement prior to first dose of study treatment. Pre-dose values on Day 1 qualify as baseline measurements.

^b Day 1 is defined as date of first dose of study treatment.

^c Complement activation panels are only collected at these time points.

^d Renal safety biomarkers and dipstick urinalysis for hematuria are not collected during follow-up period.

^e Anti-AZD8233 antibodies are collected only at these time points.

Table 4: Analysis visit windows for platelet counts

Analysis Visits	Scheduled visit day	Analysis visit window (days)
Baseline ^a	Day -28 to Day 1	≤ Day 1
Treatment period		
Visit 2 (Days 1 to 3)	Days 1 to 3	Day 1 ^b – Day 3
Visit 3 (Day 8)	Day 8	Day 4 – Day 14
Visit 5 (Day 22)	Day 22	Day 15 – Day 25
Visit 6 (Day 29)	Day 29	Day 26 – Day 36
Visit 8 (Day 44)	Day 44	Day 37 – Day 49
Visit 9 (Day 56)	Day 56	Day 50 – Day 63
Follow-up period		
Visit 10 (FUP Week 2)	Day 71	Day 64 – Day 77
Visit 11 (FUP Week 4)	Day 85	Day 78 – Day 91
Visit 12 (FUP Week 6)	Day 99	Day 92 – Day 105
Visit 13 (FUP Week 8)	Day 113	Day 106 – Day 119

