Visit 14 (FUP Week 10)	Day 127	Day 120 – Day 133
Visit 15 (FUP Week 12)	Day 141	Day 134 – Day 147
Visit 16 (FUP Week 14)	Day 155	Day 148 – Day 161
Visit 17 (FUP Week 16)	Day 169	Day 162 onwards.

^a Baseline is defined as the last measurement prior to first dose of study treatment. Pre-dose values on Day 1 qualify as baseline measurements.

^b Day 1 is defined as date of first dose of study treatment.

An early discontinuation visit (EDV) may take place at any point during the study up to Visit 9 (when the last dose of study treatment is to be administered). In this instance, follow-up visits (Week 2, Week 4 etc.) will begin at date of last administered treatment prior to study discontinuation. Analysis visit windows will be applied to follow-up visits in line with the examples above.

If there is more than one value per subject within an analysis visit window then the closest value to the scheduled visit date will be summarized, or the earlier value if the values are equidistant from the nominal visit date. Listings will display all values contributing to a time point for a subject and will highlight the value that contributed to the summary table where feasible.

For summaries showing the maximum or minimum values, the maximum/minimum value recorded on treatment will be used, regardless of where it falls in an interval. For summaries at a subject level (i.e., the maximum) all values will be included regardless of whether they appear in a corresponding visit-based summary.

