4.2.3.4 Primary Analysis of Primary Endpoint

Laboratory data will be summarized based on the Safety Analysis Set. Summaries of the individual values and change from baseline will be presented by treatment group and visit according to the principles outlined in section 3.3.1. An additional table will be presented for hematology results, displaying the percent change from baseline (i.e. the relative change), presented by treatment group and visit. The number and proportion of patients with liver enzyme abnormalities will be summarized by treatment group and visit including a summary of the maximum recorded post-baseline value. Treatment-emergent platelet count abnormalities will be summarised by treatment group and visit, including the shift to minimum value and key subject information will be presented.

The composite measure of the PFC index and corresponding ratio of AZD8233 to placebo will be presented by treatment group and visit. Box plots over time will be produced by treatment group for the composite measure and for the fold-change of the six individual biomarkers. A spaghetti plot over time of the fold-change of the six individual biomarkers will also be produced for each subject.

Shift tables will be presented for select laboratory parameters (clinical chemistry and hematology). Spaghetti plots over time will be produced for ALT, AST, TBL and gamma GPT, with the corresponding reference range overlaid on top. The following plots will be presented for platelet count only:

- Empirical cumulative distribution function curves for the absolute change from baseline to minimum value.

- A spaghetti plot of the relative change from baseline in subjects with platelet count $<150 (10^9/L)$ or $> 30\%$ decrease from baseline.
- A spaghetti plot of the absolute change from baseline in subjects with platelet count $<150 (10^9/L)$ or $> 30\%$ decrease from baseline.

Clinical laboratory data will be reported in standard international units.

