4.2.4.2 Derivations

Vital sign measurements (including weight, height and BMI), ECG and cardiac telemetry results will be assigned to analysis visits as described in Section [3.3.2](#).

Change from baseline for vital sign measurements and ECG parameters (where applicable) will be calculated for all post-baseline visits as the respective visit value minus the baseline value.

Height is measured once at baseline and this measure is used to calculate BMI at all proceeding visits.

Vital Signs

Based on the respective reference range indicators, the following flags will be applied to all vital sign measurements; ‘Normal’ (if the value is within the normal reference range), ‘Low’

(if the value is below the normal reference range) or ‘High’ (if the values is above the normal reference range).

Parameter	Normal Reference Ranges
Systolic blood pressure	80 - 140 mmHg
Diastolic blood pressure	50 -90 mmHg
Heart rate	50 - 100 bpm
Temperature	<=37°C

ECG

Outlier categories with respect to QTcF will be defined as follows:

- Absolute value > 450 ms and \leq 480 ms
- Absolute value > 480 ms and \leq 500 ms
- Absolute value > 500 ms
- Increase from baseline > 30 ms and \leq 60 ms
- Increase from baseline > 60 ms

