4.2.4.4 Primary Analysis of Primary Endpoint

Vital Signs

Vital signs will be summarized based on the Safety Analysis Set. Summaries of the individual values and change from baseline will be presented by treatment group and visit according to the principles outlined in section [3.3.1](#).

Weight, height and BMI will be listed only.

ECG

ECG parameters will be summarized based on the Safety Analysis Set. Summaries of the individual values and change from baseline will be presented by treatment group and visit according to the principles outlined in section [3.3.1](#). Outliers with respect to QTcF will be tabulated using the categories defined in Section [4.2.4.2](#).

Cardiac Telemetry

Results for 12-lead ECG real-time cardiac telemetry will be listed based on the Safety Analysis Set including the overall assessment, specifics of abnormalities and the start and stop date/time.

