4.2.5.4 Primary Analysis of Secondary Endpoint

A listing of PK blood sample collection times as well as derived sampling time deviations will be provided. A listing of urine sample collection start and stop times will be provided. Urine amount and fraction of dose excreted (by interval and cumulative) will be listed.

Pharmacokinetic Concentrations

Plasma concentrations, amount excreted in urine (Ae), and fraction of dose excreted (per collection interval and cumulative) and PK parameters will be summarized by analytes and timepoints using descriptive statistic, number of non-missing observations, n below LLOQ, arithmetic mean, SD, geometric mean, geometric coefficient of variation (CV%), min, median, max and based upon the PK analysis set.

Where the actual time that a sample was taken deviates by more than the specified time allowances from the nominal time then concentration will be excluded from the summary statistics and statistical analysis.

Nominal Time	Time allowance
Pre-dose	Up to 30 minutes prior to dosing
0.5 h post dose	± 2 minutes
1 h post dose	± 5 minutes

1.5 h post dose	± 5 minutes
2 h post dose	± 5 minutes
2.5 h post dose	± 5 minutes
3 h post dose	± 10 minutes
4 h post dose	± 10 minutes
5 h post dose	± 10 minutes
6 h post dose	± 10 minutes
8 h post dose	± 10 minutes
10 h post dose	± 30 minutes
12 h post dose	± 30 minutes
24 h post dose	± 1 hour
36 h post dose	± 1 hour
48 h post dose	± 1 hour

Data from subjects excluded from the PK population will be included in the data listings, but not in the summaries or in the inferential statistics.

For t_{max} and time of last quantifiable plasma concentration (t_{last}) only n, median, minimum and maximum will be used.

Pharmacokinetic parameters will be rounded for reporting purposes in the summary tables and subject listings, as per the PK order form provided by AZ.

Individual plasma concentrations versus actual time will be plotted by analyte in linear and semi-logarithmic scale, with separate plots for each subject and study day. Plots will be based on the PK analysis set and displayed up to 48 hours post-dose.

Combined individual plasma concentration versus actual times will be plotted by analyte and study day in linear and semilogarithmic scale. Plots will be grouped by dose level, based on the PK analysis set and displayed up to 48 hours post-dose.

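### Part C SAP 3.3.2: followed as written, the one-value-per-window rule keeps every 0.5–8 h ECG and BP/pulse value, and every post-dose complement value, out of the Visit 9 by-visit tables

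*SAP*

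**What the plan says.** Part C SAP 3.3.2 assigns ECG, vital-sign and laboratory values to analysis windows by actual date. Tables 2 and 3 give the last-dose stay a single row, "Visit 9 (Day 57 to 59", with one window running from Day 43 to Day 63. Where a participant has several values in the same window, 3.3.2 selects by this rule: "closest value to the scheduled visit date will be summarized, or the earlier value if the values are equidistant from the nominal visit date". Scheduled serial measurements are not exempted.

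The tables follow the same unit. SAP 3.3 states: "Summaries will be provided by study visit where appropriate". For vital signs and ECG, SAP 4.2.4.4 states: "Summaries of the individual values and change from baseline will be presented by treatment group and visit"; the laboratory section, 4.2.3.4, uses the same formula. For those two measures, 4.2.4.2 also defines change per visit: it "will be calculated for all post-baseline visits as the respective visit value minus the baseline value". Protocol 9.4.3 agrees: "Safety variables will be summarised by treatment group and visit using descriptive statistics". By contrast, SAP 4.2.5.4 says that "PK parameters will be summarized by analytes and timepoints".

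The Part C schedule (Protocol Table 3; SAP 7.1) has 12 ECG and 12 BP/pulse measurements around the Day 57 dose and 4 complement samples. A schedule footnote says the complement samples are timed to fall around Cmax.

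**The concern.** Vital signs, ECG and laboratory evaluations are primary endpoints of Part C, and the dense sampling after the last dose exists to show the acute response. A rule written to choose among stray values in a window, applied to scheduled serial samples, reduces that profile to one number, and the number it chooses is not an early post-dose one.

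Complement is the clearest case. The protocol's risk table describes complement activation as a class effect driven by Cmax, and the samples are timed accordingly. A Visit 9 complement table that contains only values taken before the last dose cannot show a response to that dose. For BP/pulse and complement the SAP names no maximum or minimum summary. One is named for liver enzymes ("including a summary of the maximum recorded post-baseline value", 4.2.3.4), and platelets have a shift to the minimum. Without a time-point table, the serial BP/pulse and complement values could be visible only in listings and range flags.

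**Working it through.** The plan states no figure on this point, so the check applies the stated rule to the stated schedule.

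**Inputs**
- ECG and BP/pulse at Visit 9: pre-dose, then 0.5, 1, 2, 3, 4, 6, 8, 12, 24, 36 and 48 h (12 values, 7 of them from 0.5 to 8 h). Complement: pre-dose, then 1, 2 and 4 h (Protocol Table 3).
- Dosing on Day 57, with a window of 1 day either side (Protocol section 8, Visit 9): Day 56, 57 or 58.
- Scheduled date: the SAP gives a range, so four readings were tried: Day 57, anywhere in Days 57–59, the midpoint Day 58, and Day 59.
- Clock time: not stated. Pre-dose lipid samples are taken fasting in the morning, and Part C pre-dose assessments may be done within 30 minutes before dosing, so morning dosing (08:00 to 11:45) is assumed. The pre-dose value was set 15 minutes before dosing.

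**Rule**
- Date of a value taken h hours after dosing = dosing day + floor((clock hour of dosing + h) / 24).
- Distance = 0 if that date lies on or within the scheduled date, otherwise the number of days to the nearest scheduled day.
- Select the smallest distance; if tied, the earliest value.

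**Worked case: dosing on Day 57 at 09:00.** The pre-dose to 12 h values (9 of them) fall on Day 57, the 24 and 36 h values on Day 58, and the 48 h value on Day 59. Scheduled Day 57: nine values tie, so pre-dose is selected. Days 57–59: all 12 tie, so pre-dose. Day 58: 24 and 36 h tie, so 24 h. Day 59: 48 h.

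**All combinations, ECG and BP/pulse**

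| Scheduled date read as | Dose Day 56 | Dose Day 57 | Dose Day 58 |
|---|---|---|---|
| Day 57 | 24 h | pre-dose | pre-dose |
| Days 57–59 | 24 h | pre-dose | pre-dose |
| Day 58 | 48 h | 24 h | pre-dose |
| Day 59 | 48 h | 48 h | 24 h |

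Pre-dose is selected in 5 of the 12 cells, 24 h in 4, 48 h in 3, and a 0.5–8 h value in none. The cells are a check over possible readings, not a frequency.

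The reason is general. With dosing no later than 11:45, the 8 h value falls no later than 19:45, so every 0.5–8 h value shares its date with the pre-dose value and loses the tie to it. All four complement samples share one date for the same reason, so pre-dose is selected in 12 of 12 cells.

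**What this removes from the tables.** With about 11 participants: 7 × 11 = 77 values from 0.5 to 8 h per ECG or BP/pulse parameter, and 3 × 11 = 33 post-dose values per complement analyte.

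**Where the result changes**
- Pre-dose value missing, dosing on Day 57: complement selects 1 h. ECG and BP/pulse select 0.5 h if the scheduled date is Day 57 or Days 57–59, 24 h if Day 58, and 48 h if Day 59.
- Later dosing on Day 57 with the Day 58 reading: 12 h for dosing at 12:00 or 14:00, 8 h at 16:00, 6 h at 18:00.

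**Visit 2.** Here the Day 1 pre-dose value is baseline. If the scheduled date is read as Day 1 or Days 1–3, with morning dosing, the rule keeps the first post-dose value: ECG 0.5 h (10 of 11 left out), BP/pulse 0.25 h (13 of 14), complement 1 h (2 of 3), renal biomarkers 24 h (1 of 2). Later nominal days were not run for Visit 2.

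**The case against.** The strongest reply is that the SAP may intend tabulation by time point, in which case nothing is left out. Part C 4.2.3.2 computes laboratory change at every post-baseline time point and defines the renal fold change at a given time point. Protocol 9.4.1 allows summaries by time point of assessment as appropriate, and the by-visit sentence in Part C 3.3 is itself qualified by where appropriate. Protocol 8.2.3 presents ECG statistics by time point, though under Part B. Table shells, which are not in these documents, may settle the layout.

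Some of this stands: the wording is mixed, most of all for laboratory data, and the intent may be sound. It does not cure the text. Footnotes c and e to Part C Table 3 use time points to mean visits. The sentence on listings in 3.3.2 has several values contributing to a time point, with the one that reached the summary table highlighted. ECG and vital-sign change is defined per visit. PK is expressly tabulated by time point; these measures are not.

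The second reply is that little depends on these tables. Part C has about 11 participants, no hypothesis test and only descriptive output. Clinically relevant ECG, laboratory and vital-sign changes are captured as adverse events, and the stopping criteria do not use by-visit tables. This stands and limits the severity.

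A reader might also infer more than the documents support:
- **That post-dose data are lost.** They are not. Listings show all values, telemetry is listed, the Normal/Low/High flags apply to all laboratory and vital-sign measurements, and subject-level maximum/minimum summaries use every value (3.3.2).
- **That the QTcF outlier table is affected.** SAP 3.3.2 and 3.3.3 point to use of all values in subject-level and abnormality summaries, and 4.2.4.4 does not restrict that table to by-visit values.
- **That the protocol predicts acute ECG or blood-pressure effects in Part C.** The statement in Protocol 4.3 about Cmax-related risks soon after dosing sits under Part A and names only aPTT. Direct Cmax support exists for complement alone.
- **That Part A has the same defect.** It has the same selection rule, but its 3.3 speaks of time point of assessment, so it is ambiguous.

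**Conclusion.** The concern holds in a limited form. As written, the Part C rule yields Visit 9 by-visit tables with no 0.5–8 h ECG or BP/pulse value and only the pre-dose complement value. This is a stated rule that gives a poor result for serial samples, rather than a missing detail, and two programmers could build different primary-endpoint tables from the same SAP. The result rests on complete data, morning dosing, selection by calendar date, and no overriding instruction in the table shells. It affects only the descriptive by-visit mean and change-from-baseline tables. Severity is minor to moderate.

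**What to change.** Add to Part C SAP 3.3.2:

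> Scheduled serial ECG, vital-sign, complement and (Visit 2) renal-biomarker values at Visits 2 and 9 are summarised by treatment group, visit and nominal time point. The closest/earlier rule applies only to repeat or unscheduled values within the same nominal time point.

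Use the same wording in the Part A SAP for consistency. A sentence confirming that the QTcF outlier table uses all post-dose values is optional.

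The cost is SAP text and longer tables: at Visit 9, 12 time points instead of 1 for each ECG and BP/pulse parameter, and 4 instead of 1 for each complement analyte. No new data are needed and study conduct does not change.

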3.3.1.3 Study Periods

For listings of adverse events, lipid levels, laboratory values, vital signs and electrocardiogram (ECG), values will be allocated to a study period. The allocation to the study periods will be performed after any imputation of missing dates (for AEs only) as described in Section 3.3.1.2. The study periods are defined as follows:

- Pre-treatment: Up to 28 days prior to administration of study drug (Day <1).
- Treatment Period: From Day 1 to date of last dose + 2 days (from visit 2 up to visit 9).
- Follow-up Period: From day of last dose + 3 days onwards (visit 10 to visit 17).

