3.3.3 Handling of Unscheduled Visits

Visits that fall outside the visit windows defined in the CSP will be classified as Unscheduled Visits. Unscheduled visits will be numbered sequentially with an increment of 0.1. For example, if two measurements are done in an unscheduled visit that occurs between Day 3 and Day 8, then these visits will be numbered UNS 2.1 and 2.2 in the order they occurred. The values measured at unscheduled visits will not be included in the by-visit summary tables, they will be included in the overall summary tables (for abnormalities, minimum/maxima etc.) and will be presented in the listings.

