Aspartate aminotransferase (AST), alanine aminotransferase (ALT) and total bilirubin (TBL) will be categorised as follows:

AST and ALT:

- $<3 \times$ upper limit of normal (ULN) (or below the LLOQ).
- ≥ 3 to $<5 \times$ ULN.
- ≥ 5 to $<8 \times$ ULN.
- $\geq 8 \times$ ULN.

TBL:

- $<1 \times$ ULN (or below the LLOQ).
- ≥ 1 to $<2 \times$ ULN.
- $\geq 2 \times$ ULN.

Occurrences of AST or ALT $\geq 3 \times$ ULN together with TBL $\geq 2 \times$ ULN are reported as SAE (Potential Hy's Law).

Platelet count

Platelet count will be classified as follows:

- $< LLN$
- $> ULN$
- $< 50 (10^9/L)$

- < 75 ($10^9/L$)
- < 100 ($10^9/L$)
- < 150 ($10^9/L$)
- > 30% decrease from baseline
- < 150 ($10^9/L$) and > 30% decrease from baseline.

Shift to minimum value on-treatment value for platelet count will be classified as follows:

- < 50 ($10^9/L$)
- ≥ 50 and < 75 ($10^9/L$)
- ≥ 75 and < 100 ($10^9/L$)
- ≥ 100 and < 150 ($10^9/L$)
- ≥ 150 ($10^9/L$)

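### Does leaving on-treatment undefined in SAP Part C cut the follow-up platelet counts out of the shift-to-minimum table?

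*SAP*

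**What the plan says.** Platelet count is named in the Part C primary safety endpoint (Protocol Section 3, Table 5). SAP Part C handles its minimum in several places:

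- Section 3.3.2, general rule for extremes: "the maximum/minimum value recorded on treatment will be used, regardless of where it falls in an interval".
- Section 3.3.2, next sentence: "For summaries at a subject level (i.e., the maximum) all values will be included regardless of whether they appear in a corresponding visit-based summary".
- Section 3.3.3, on unscheduled values: "they will be included in the overall summary tables (for abnormalities, minimum/maxima etc".
- Section 4.2.3.2: "Shift to minimum value on-treatment value for platelet count will be classified as follows", followed by five bands from below 50 to 150 and above.
- Section 4.2.3.4: the shift to minimum is reported within the summary of treatment-emergent platelet abnormalities. The same section asks for a cumulative distribution plot of change to the minimum, which has no on-treatment label.

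No definition of on-treatment appears. The nearest text is in Section 3.3.1.3: "Treatment Period: From Day 1 to date of last dose + 2 days (from visit 2 up to visit 9", then "Follow-up Period: From day of last dose + 3 days onwards (visit 10 to visit 17". The stated scope of these periods is "For listings of adverse events, lipid levels, laboratory values, vital signs and electrocardiogram (ECG), values will be allocated to a study period". In Section 3.3.2, "Table 4: Analysis visit windows for platelet counts" also groups visits under a treatment heading (last window Days 50 to 63) and a follow-up heading (Visits 10 to 17).

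**The concern.** A reader who meets an undefined on-treatment minimum looks for the closest period definition and finds one that ends two days after the last dose. All eight counts scheduled after the third dose fall in what the SAP calls follow-up, so that reading empties the nadir table of post-dose-3 data.

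Thrombocytopenia is the first risk in the protocol's risk table, and one severe case occurred in a primate study of AZD8233. Protocol Section 4.2 gives a plasma half-life of 2 to 3 weeks, so a two-day cut-off is only 2/21 to 2/14, or about 10% to 14%, of one half-life. Exposure continues well past it. The liver maximum in the same SAP section is taken over all post-baseline values, so a shorter window for platelets alone would be hard to justify.

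**Working it through.** The plan states no figure on this point, so there is none to reproduce. The check is a count of scheduled samples, followed by a comparison of the texts.

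**Inputs.** Part C doses fall on Days 1, 29 and 57 (Protocol Section 6.1.1, Table 6). Dedicated post-baseline platelet samples come from SAP Part C Section 7.1 and Table 4:

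- Treatment visits: Days 2, 3, 8, 22, 29, 44 and 56, giving 7.
- Follow-up visits: 57 + 14k for k = 1 to 8, that is Days 71, 85, 99, 113, 127, 141, 155 and 169, giving 8.
- Total: 7 + 8 = 15.

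**Candidate end dates for a participant given all three doses.** Section 3.3.1.3 gives 57 + 2 = Day 59. Table 4 gives Day 63. The earliest in-window Visit 10 is 71 − 2 = Day 69, which is beyond both.

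| End of on-treatment | Counts kept | After dose 3 |
|---|---|---|
| Day 59 | 7 of 15 (47%) | 0 |
| Day 63 | 7 of 15 (47%) | 0 |
| End of study | 15 of 15 | 8 |

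The haematology panel adds only the Day 57 pre-dose count, which makes the narrow result 8 of 16, still with none after dose 3. The Week 16 platelet mark is unclear in Protocol Table 3 as extracted. Without that sample the narrow result is 7 of 14. For an early discontinuer, the last dose + 2 days cut-off keeps Days 2 and 3 if dose 1 was the last, and five counts (Days 2, 3, 8, 22, 29) if dose 2 was the last.

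**Which end date does the text support?** The three SAPs share much of their wording, so they can be compared directly.

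| | General rule for extremes (3.3.2) | Study periods (3.3.1.3) | Platelet minimum |
|---|---|---|---|
| Part A | on treatment | split at last dose + 2 days | any post-baseline value (4.2.3.4) |
| Part B | on treatment | on-treatment runs from Day 1 to end of study | on-treatment shift (4.3.3.1) |
| Part C | on treatment | split at last dose + 2 days | on-treatment shift (4.2.3.2) |

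- Part A has the same rule and the same period split as Part C, yet its platelet minimum is post-baseline. The split was therefore not meant to limit the minimum there.
- Part C's shift line repeats Part B's, including the duplicated word value. The amendment histories date the platelet additions to 12 April 2022 in Part B and 12 September 2022 in Part C. Wording that appears to be carried over from Part B most naturally keeps Part B's meaning.
- Within Part C, the rule in Section 3.3.2 also covers maxima, yet Section 4.2.3.4 takes the liver maximum post-baseline. The authors seem to use the two terms interchangeably.
- Treatment-emergent, the label over the shift summary, is defined only for adverse events (Section 4.2.1.1): onset on or after the first dose, with no end date.

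**What remains visible on the narrow reading?** By-visit platelet abnormality summaries use Table 4 windows that run to Visit 17. The individual plots of participants below 150 or with more than a 30% fall have no on-treatment limit. Values are also listed, including unscheduled ones.

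**The case for a change.** The strongest case for acting is that the term is undefined and two adjacent sentences in Section 3.3.2 pull in different directions. The wording seems to have been copied from Part B without its definition, into a document whose own periods separate treatment from follow-up. Identically worded tables could then cover Days 1 to 169 in Part B and Days 1 to 59 in Part C. The listings scope does not fully settle this, because Part B's end-of-study definition is introduced for listings too. A short clarification would cost almost nothing.

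Most of this stands as description: the term is undefined, the narrow reading is possible, and the 7 of 15 is correct if that reading is used. Two parts do not carry the conclusion. First, the appeal to timing is weaker than it looks. Protocol Section 4.3 speaks of platelet reduction after more than 3 months of dosing, in Part A text about other antisense programmes. Part C dosing ends on Day 57, so no Part C count follows 3 months of dosing. Second, an undefined term matters only if a competent analyst would be led to the wrong result. Here the neighbouring sentences, the liver rule and both sister SAPs lead to the right one. The loss in the cumulative distribution plot is conjecture, since that plot has no on-treatment limit.

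**Conclusion.** This is a missing definition that analysts would fill sensibly, and no change to the plan follows. On the better-supported reading, any value after the first dose to the end of the study, nothing is lost: 15 of 15 dedicated counts enter the platelet minimum. On the least favourable reading, 8 of 15 counts (53%) drop out of one shift table and arguably one plot. Part C is descriptive, with about 11 participants randomized 8:3 and no hypothesis test, and every late fall would still be shown by visit, by participant and in listings. The safety conclusion would rest on the same data either way.

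This rests on three assumptions: the by-visit tables, individual plots and listings are produced as planned; the counts follow the schedule in SAP Part C; and the shared wording across the three SAPs carries a shared meaning. The third is an inference from the texts, not something SAP Part C states.
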